Appendix 7. Blood Sampling Summary

This table summarizes the approximate number of samples and blood volumes for all blood sampling (screening, safety laboratories, bioanalytical assays, and the other tests) during the study.

Protocol I8F-JE-GPGC Sampling Summary

Purpose	Blood Volume per Sample (mL)	Number of Blood Samples		Total Volume (mL)	
		Cohort 1 or 2	Cohort 3	Cohort 1 or 2	Cohort 3
Screening serology and Serum pregnancy tests ^a	9 ^b	1	1	9	9
Clinical safety laboratory tests ^a	10 ^b	20	16	200	160
Lipid panel	2.5	3	3	7.5	7.5
LY3298176 pharmacokinetics	3	18	18	54	54
Potential additional LY3298176 pharmacokinetic samples	3	3	3	9	9
Glucagon	2	15	13	30	26
Fasting plasma glucose and insulin	4.5	15	13	67.5	58.5
Oral glucose tolerance test (serum glucose and insulin)	2.5	10	10	25	25
HbA1c	2	4	4	8	8
Immunogenicity	6	4	4	24	24
Exploratory storage sample ^d					
Adiponectin	2	2	2	4	4
Cortisol	2.5	3	3	7.5	7.5
Bone biomarkers	3.5	2	2	7	7
Pharmacogenetics	6	1	1	6	6
Nonpharmacogenetics Storage sample	4.5	6	6	27	27
Total				485.5 ^c	432.5 ^c

Abbreviation: HbA1c = hemoglobin A1c.

^a Additional samples may be drawn if needed for safety purposes.

^b Because screening and safety (chemistry and hematology) tests are performed at local laboratories at each site, this volume is an estimate and will vary depending on the local laboratory's testing requirements.

^c The maximum blood volume will increase if follow-up visits for antidrug antibody testing are needed.

^d Blood volumes for this storage sample is calculated based on the assumption that the following biomarkers will be assayed for.

Appendix 8. Protocol I8F-JE-GPGC Blinding/Unblinding Plan

Levels of unblinding are indicated in the table below. This table provides general guidance as to who will be allowed access to randomization codes at various steps of the trial. The information in the protocol will always take precedence over this table.

Randomization data are kept strictly confidential and are accessible only by authorized personnel until unblinding of the trial as described below. All measures possible must be taken to maintain the blinded portion of the study, which means that access to the randomization code must be restricted to authorized personnel as described in the protocol and summarized in the table below.

If there is a need for unblinding of select people from Lilly and/or the third-party organization who are not dealing with the site, the detailed process, including formation of the unblinded team, creating restricted access electronic folders, and measures taken to guard against inappropriate dissemination of treatment codes (for example, by maintaining no contact with the study team until team is unblinded), will be described in the Unblinding Plan or another appropriate document, and approval will be sought from Lilly and Covance team statisticians.

Study I8F-JE-GPGC Blinding and Unblinding Plan

Study Team Member	Study Timelines				
	Screening	Randomization	Treatment Phase	Follow-Up	Database Lock (up to Day 85)
General					
Drug supply	NA	U	U	U	U
Randomization statisticians	NA	U	U	U	U
ECG reader	NA	B	B	B	U
Bioanalysis lab/sample analysis	NA	U	U	U	U
Clinical Site					
Pharmacist	NA	U	U	U	U
Dosing staff	NA	B	B	B	U
Patient	NA	B	B	B	U
Investigator	NA	B	B	B	U
Study monitor	NA	U	U	U	U
Covance					
Project integration	NA	U	U	U	U
Data management	NA	U	U	U	U
Programming	NA	U	U	U	U
Statistician	NA	U	U	U	U
Medical writing	NA	U	U	U	U
Pharmacokinetic scientist/associate	NA	U	U	U	U
Lilly					
CPM	NA	U	U	U	U
CPA	NA	U	U	U	U
DSA	NA	U	U	U	U
SDTM core team	NA	U	U	U	U
Statistician	NA	U	U	U	U
Medical writing	NA	U	U	U	U
Clinical pharmacologist	NA	U	U	U	U
Pharmacokinetic scientist/associate	NA	U	U	U	U

Abbreviations: B = blinded; CPA = clinical pharmacology associate; CPM=clinical project management; DSA = data sciences associate; ECG = electrocardiogram; lab = laboratory; NA = not applicable; SDTM = study data tabulation model; U = unblinded.

**Appendix 9. Protocol Amendment I8F-JE-GPGC(a)
Summary****A Multiple-Ascending Dose Study in Japanese Patients
with Type 2 Diabetes Mellitus to Investigate the Safety,
Tolerability, Pharmacokinetics, and Pharmacodynamics
of LY3298176**

Overview

Protocol I8F-JE-GPGC, A Multiple-Ascending Dose Study in Japanese Patients with Type 2 Diabetes Mellitus to Investigate the Safety, Tolerability, Pharmacokinetics, and Pharmacodynamics of LY3298176, has been amended. The new protocol is indicated by Amendment (a) and will be used to conduct the study in place of any preceding version of the protocol.

The overall changes and rationale for the changes made to this protocol are as follows:

- The study will be unblinded triggered by the database lock with data up to Day 85 to initiate the subsequent Japan clinical studies.

The overall changes and rationale for the changes made to this protocol are described in the following table:

Table GPGC.3. Amendment Summary for Protocol I8F-JE-GPGC Amendment(a)

Section # and Name	Description of Change	Brief Rationale
7.3. Blinding and Appendix 8. Protocol I8F-JE-GPGC Blinding/Unblinding Plan	Blinded period ends when the database is locked with data up to Day 85.	To initiate the subsequent clinical studies, the unblinded data of GPGC study up to Day 85 will be provided to ERBs and investigators for better understanding the profile of LY3298176 in Japanese patients with T2DM.

Revised Protocol Sections

Note: All deletions have been identified by ~~strikethroughs~~.
 All additions have been identified by the use of underscore.

7.3. Blinding

Blinding will be maintained until the database is locked with data up to Day 85 (blinded period) ~~throughout the conduct of the study~~ as described in the separate Blinding Plan (Appendix 8).

If a patient's study treatment assignment is unblinded during the blinded period, the patient must be discontinued from the study unless the investigator obtains specific approval from a Lilly clinical pharmacologist, CRP, or CRS for the study participant to continue in the study. During the study, emergency unblinding should occur only by accessing the study patient's emergency code.

In case of an emergency, the investigator has the sole responsibility for determining if unblinding of a patient's treatment assignment is warranted for medical management of the event. The patient's safety must always be the first consideration in making such a determination. If the investigator decides that unblinding during the blinded period is warranted, it is the responsibility of the investigator to promptly document the decision and rationale and notify Lilly as soon as possible.

Appendix 8. Protocol I8F-JE-GPGC Blinding/Unblinding Plan

Study Team Member	Study Timelines				
	Screening	Randomization	Treatment Phase	Follow-Up	Database Lock up to Day 85
General					
Drug supply	NA	U	U	U	U
Randomization statisticians	NA	U	U	U	U
ECG reader	NA	B	B	B	UB
Bioanalysis lab/sample analysis	NA	U	U	U	U
Clinical Site					
Pharmacist	NA	U	U	U	U
Dosing staff	NA	B	B	B	UB
Patient	NA	B	B	B	UB
Investigator	NA	B	B	B	UB
Study monitor	NA	U	U	U	U

Leo Document ID = 0cb9e08a-d783-42f0-97e6-8c6c45ee1db0

Approver: PPD

Approval Date & Time: 15-Oct-2018 01:38:16 GMT

Signature meaning: Approved

Approver: PPD

Approval Date & Time: 15-Oct-2018 04:19:51 GMT

Signature meaning: Approved

2. ABBREVIATIONS

Abbreviations pertain to the Statistical Analysis Plan (SAP) only (not the tables, figures and listings [TFLs]).

| | |
|------------------|---|
| ADA | Antidrug antibody |
| AE | Adverse event |
| ALP | Alkaline phosphatase |
| ALT | Alanine aminotransferase |
| AUC | Area under the concentration versus time curve |
| AUC(0- τ) | Area under the concentration versus time curve during one dosing interval (168 hours) |
| BQL | Below the lower limit of quantitation |
| CI | Confidence interval |
| C _{max} | Maximum observed drug concentration |
| CL/F | Apparent total body clearance of drug calculated after extra-vascular administration |
| CRF | Case Report Form |
| CRP | Clinical research physician |
| CRS | Clinical research scientist |
| CSR | Clinical Study Report |
| CRU | Clinical Research Unit |
| CV | Coefficient of variation |
| DPP | Dipeptidyl peptidase |
| EC | Early Clinical |
| ECG | Electrocardiogram |
| e.g. | For example (Latin: exempli gratia) |
| HbA1c | hemoglobin A1c |
| ICH | International Council on Harmonisation |
| IMP | Investigational medicinal product |
| LLOQ | Lower limit of quantification |
| MAD | Multiple ascending dose |
| MedDRA | Medical Dictionary for Regulatory Activities |

| | |
|----------------|--|
| MRE | Magnetic resonance elastography |
| OGTT | Oral glucose tolerance test |
| PD | Pharmacodynamics |
| Peak to trough | Ratio of C_{\max} to C_{\min} (at 168 hours) |
| PG | Plasma glucose |
| PK | Pharmacokinetic |
| QW | Once a week |
| RA | Accumulation ratio based on $AUC(0-\tau)$ |
| SAE | Serious AE |
| SAP | Statistical Analysis Plan |
| SC | Subcutaneous |
| SD | Standard deviation |
| SMPG | Self monitored plasma glucose |
| TBL | Total bilirubin |
| T2DM | Type 2 diabetes mellitus |
| TEAE | Treatment-emergent adverse event |
| TFLs | Tables, Figures, and Listings |
| $t_{1/2}$ | Half-life associated with the terminal rate constant (λ_z) in non-compartmental analysis |
| t_{\max} | Time of maximum observed drug concentration |
| ULN | Upper limit of normal |
| V_z/F | Apparent volume of distribution during the terminal phase after extra-vascular administration |
| WHO | World Health Organization |

3. INTRODUCTION

This SAP has been developed after review of the Clinical Study Protocol (final version dated 24 August 2017).

This SAP describes the planned analysis of the safety, tolerability, pharmacokinetic (PK) and pharmacodynamic (PD) data from this study. A detailed description of the planned TFLs to be presented in the clinical study report (CSR) is provided in the accompanying TFL shell document.

The intent of this document is to provide guidance for the statistical analyses of PK and PD data. In general, the analyses are based on information from the protocol, unless they have been modified by agreement between Eli Lilly and Company and Covance Early Clinical (EC) Biometrics. A limited amount of information concerning this study (e.g., objectives, study design) is given to help the reader's interpretation. This SAP must be signed off prior to first patient administration for this study. When the SAP and TFL shells are agreed upon and finalized, they will serve as the template for this study's CSR.

This SAP supersedes the statistical considerations identified in the protocol; where considerations are substantially different, they will be so identified. If additional analyses are required to supplement the planned analyses described in this SAP, they may be performed and will be identified in the CSR. Any substantial deviations from this SAP will be agreed upon between Eli Lilly and Company and Covance EC Biometrics and identified in the CSR. Any minor deviations from the TFLs may not be documented in the CSR.

This SAP is written with consideration of the recommendations outlined in the International Council on Harmonisation (ICH) E9 Guideline entitled Guidance for Industry: Statistical Principles for Clinical Trials¹ and the ICH E3 Guideline entitled Guidance for Industry: Structure and Content of Clinical Study Reports².

4. STUDY OBJECTIVES AND ENDPOINTS

4.1 Primary Objective

- To investigate the safety and tolerability of LY3298176 after multiple subcutaneous (SC) doses administered to Japanese patients with type 2 diabetes mellitus (T2DM).

Endpoint: Adverse events (AEs)

4.2 Secondary Objectives

- To characterize the PK of LY3298176 after multiple SC doses in Japanese patients with T2DM.

Endpoints: Area under the concentration versus time curve (AUC) and maximum observed drug concentration (C_{max}) of LY3298176

- To investigate the PD effect of LY3298176 after multiple SC doses administered to Japanese patients with T2DM.

Endpoints: Fasting plasma glucose levels

4.3 Exploratory Objectives

- To investigate the exploratory PD effects of LY3298176 after multiple SC doses administered to Japanese patients with T2DM.

Endpoints: Body weight, oral glucose tolerance test (OGTT) (serum glucose and insulin), 7-point self-monitored plasma glucose (7-p SMPG), hemoglobin A1C (HbA1c), lipids, glucagon, subjective appetite sensation

- To evaluate the impact of formation of antidrug antibodies (ADAs) on LY3298176 after multiple SC doses administered to Japanese patients with T2DM.

Endpoint: Presence of ADAs to LY3298176

5. STUDY DESIGN

This study is a Phase 1, multiple-site, patient- and investigator-blind, placebo-controlled, randomized, parallel dose–group, 8-week multiple ascending dose (MAD) study in Japanese patients with T2DM.

Figure 1 illustrates the study design.

[figure not shown]

Figure 1. Illustration of study design

This study consists of 3 cohorts. Patients will be randomized to 3 treatment regimens or placebo within each cohort, including up to 3 dose levels of LY3298176 in each regimen, as shown in Figure 1. Patients will be administered 8 weekly SC doses of LY3298176 or placebo.

Screening to Prestudy

Patient eligibility for this study will be determined at a screening visit. Eligible patients will visit the clinical research unit (CRU) before Day -1 to receive training on the 7p-SMPG, glucose meters, test strips, and diaries. Patients will conduct the 7-point SMPG until the day before Day -1. In addition, patients treated with metformin or dipeptidyl peptidase intravenous (DPP-IV) inhibitors (except for omarigliptin, trelagliptin, and linagliptin) will be required to withdraw their treatment and have at least a 28-day washout period before dosing with investigational medicinal product (IMP). These patients will be required to monitor their plasma glucose (PG) levels during the washout period.

Treatment Period

Patients will be admitted to the CRU on Day -1. If the investigator decides not to administer the first dose to a patient on a particular day based on the results of medical assessments, vital signs, or electrocardiograms (ECGs), the patient may be rescheduled to participate in the study, and any procedures performed up to that point may be repeated.

Patients will be given SC doses of LY3298176 (or placebo) on Days 1, 8, 15, 22, 29, 36, 43, and 50 after an overnight fast (at least 8 hours). Even if there are visit allowances of ± 1 day, the interval of each IMP administration must be at least 6 days.

Patients in Cohort 1 will receive either LY3298176 with titration regimen starting from 2.5 mg for Days 1 and 8 followed by 5 mg for Days 15 and 22, and 10 mg for Days 29, 36, 43, and 50, or corresponding volume-matched placebo. Patients in Cohort 2 will receive either LY3298176 with titration regimen starting from 5 mg for Days 1 and 8 followed by 10 mg for Days 15, 22, 29, and 36, and 15 mg for Days 43 and 50, or corresponding volume-matched placebo. Patients in Cohort 3 will receive either 5 mg LY3298176 or placebo for 8 weeks. The planned highest dose or dosing regimen of Cohort 2 may be changed for the reason of tolerability.

If the investigator decides not to up-titrate the dose level of IMP for individual patients in the titration regimen in Cohorts 1 or 2 for the reason of safety and/or tolerability, patients may keep current dose level to the planned last dose at Day 50 and will no longer be allowed up-titration during the treatment period. Down-titration is not allowed during the treatment period for any patients in Cohorts 1, 2, or 3.

Safety, as assessed by AEs, vital signs, 12-lead ECGs, concomitant medications, safety laboratory measurements, and medical assessments from at least 8 patients (to include at least 5 on LY3298176) up to Day 36 predose procedure of Cohort 1, will be reviewed by the sponsor and investigator before dose-escalation decision to Cohort 2.

Dosing will be staggered in Cohorts 1 and 2 so that an initial group of up to 6 patients receiving LY3298176 and 2 patients receiving placebo will be dosed. On Days 4 and 32 of Cohort 1 and on Days 4, 18, and 46 of Cohort 2, the investigator and Lilly clinical pharmacologist, clinical research physician (CRP), or clinical research scientist (CRS) will review available safety data from these patients, and if no relevant safety signals are noted, the remaining patients will be dosed. Patients in Cohort 3 will be dosed after evaluation of safety data of the initial staggered group of Cohort 2.

PK sampling and safety assessments, including AEs, concomitant medications, medical assessments, clinical laboratory tests, vital signs, and ECGs, will be performed according to the Schedule of Activities.

The investigator or qualified designee will review all available inpatient safety data before discharging patients from the CRU on the morning of each planned discharging day provided they are deemed medically fit by the investigator. Patients may be required to remain at the CRU longer than the planned discharging day at the investigator's discretion to assure patients' safety or to provide additional safety monitoring. Patients will be discharged after the review of all final safety assessments from the last follow-up visit is completed by the investigator.

Follow-Up Period

Safety follow-up visits will occur approximately 2 and 5 weeks after the last dose of IMP. Patients who have treatment-emergent LY3298176 ADAs at the planned follow-up visit (Day 85) or early termination visit may be monitored until return to baseline.

6. TREATMENTS

The following is a list of the study treatment abbreviations and treatment regimens that will be used in the TFLs.

| Cohort | Study Treatment Name | Treatment order in TFL |
|---------------|-----------------------------|-------------------------------|
| 1-3 | Placebo | 1 |
| 1 | 2.5 mg LY3298176 | 2 |
| | 5 mg LY3298176 | 3 |
| | 10 mg LY3298176 | 4 |
| 2 | 5 mg LY3298176 | 5 |
| | 10 mg LY3298176 | 6 |
| | 15 mg LY3298176 | 7 |
| 3 | 5 mg LY3298176 | 8 |

The treatment regimens used will be:

| Study Treatment Regimen | Treatment order in TFL |
|-----------------------------|------------------------|
| Placebo QW | 1 |
| 2.5 mg – 10 mg LY3298176 QW | 2 |
| 5 mg – 15 mg LY3298176 QW | 3 |
| 5 mg LY3298176 QW | 4 |

7. SAMPLE SIZE JUSTIFICATION

The sample size for the study was chosen to provide sufficient data to evaluate the primary objective of this study and is not intended to achieve any a priori statistical requirements.

Approximately 49 Japanese patients with T2DM may be enrolled so that approximately 32 patients complete the study with compliant defined dosing regimen. The estimated drop-out rates are 30% for Cohorts 1 and 3 and 50% for Cohort 2. Patients will be administered 8 weekly SC doses of LY3298176 or placebo in a ratio of 12 LY3298176 : 3 placebo for Cohorts 1 and 3, and 16 LY3298176 : 3 placebo for Cohort 2. Considering the possibility of higher drop-out rate when administered the highest dose level of LY3298176, the number of patients to be enrolled in Cohort 2 is higher than those for the other 2 cohorts.

Replacement of discontinued patients is not planned because the sample size is determined considering the expected drop-out rate.

8. DEFINITION OF ANALYSIS POPULATIONS

The “Safety” population will consist of all enrolled patients, whether or not they completed all protocol requirements.

The “Pharmacokinetic” population will consist of all patients who received at least one dose of IMP and have evaluable PK data.

The “Pharmacodynamic” population will consist of all patients who received at least one dose of IMP and have evaluable PD data.

Patients treated with placebo will be pooled for PD and safety analyses.

All protocol deviations that occur during the study will be considered for their severity/impact and will be taken into consideration when patients are assigned to analysis populations.

Additional analyses will be conducted on the basis of the treatment groups defined by titration regimen as actually treated, if deemed necessary, after data review.

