5.1. Overall Design

Study GPGC is a Phase 1, multiple-site, patient- and investigator-blind, placebo-controlled, randomized, parallel dose–group, 8-week MAD study in Japanese patients with T2DM.

Study governance considerations are described in detail in [Appendix 3](#).

[Figure GPGC 5.1](#) illustrates the study design.

[figure not shown]

Figure GPGC 5.1. Illustration of study design for Protocol I8F-JE-GPGC.

This study consists of 3 cohorts. Patients will be randomized to 4 treatment groups, including 3 dose levels of LY3298176 and placebo as shown in [Figure GPGC 5.1](#). Patients will be administered 8 weekly SC doses of LY3298176 or placebo. Study procedures and timing for prestudy, treatment, and follow-up phases are outlined in [Section 2](#).

Screening to Prestudy

Patient eligibility for this study will be determined at a screening visit. Eligible patients will visit the clinical research unit (CRU) before Day -1 to receive training on the 7-point self-monitored plasma glucose (SMPG), glucose meters, test strips, and diaries. Patients will conduct the 7-point SMPG until the day before Day -1. In addition, patients treated with metformin or DPP-IV inhibitors (except for omarigliptin, trelagliptin, and linagliptin) will be required to withdraw their treatment and have at least a 28-day washout period before dosing with investigational medicinal product (IMP). These patients will be required to monitor their plasma glucose (PG) levels during the washout period.

Treatment Period

Patients will be admitted to the CRU on Day -1. If the investigator decides not to administer the first dose to a patient on a particular day based on the results of medical assessments, vital signs, or electrocardiograms (ECGs), the patient may be rescheduled to participate in the study, and any procedures performed up to that point may be repeated.

Patients will be given SC doses of LY3298176 (or placebo) on Days 1, 8, 15, 22, 29, 36, 43, and 50 after an overnight fast (at least 8 hours). Even if there are visit allowances of ± 1 day, the interval of each IMP administration must be at least 6 days.

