10.3. Statistical Analyses

Statistical analysis of this study will be the responsibility of Eli Lilly and Company or its designee.

PK and PD analyses will be conducted on data from all patients who receive at least 1 dose of the IMP and have evaluable PK and PD data.

Patients treated with placebo within each cohort of the study will be pooled for PD and safety analyses.

Safety analyses will be conducted for all enrolled patients, whether or not they completed all protocol requirements. Primary safety analyses will be conducted by treatment group defined by intended titration regimen group. Additional analyses will be conducted on the basis of the treatment groups defined by titration regimen as actually treated, if deemed necessary after data review.

Additional exploratory analyses of the data will be conducted as deemed appropriate. Statistical analyses will be fully detailed in the statistical analysis plan.

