DPP	dipeptidyl peptidase

ECG	electrocardiogram
eCRF	electronic case report form
enroll	The act of assigning a patient to a treatment. Patients who are enrolled in the study are those who have been assigned to a treatment.
enter	Patients entered into a study are those who sign the informed consent form directly or through their legally acceptable representatives.
ERB	ethical review board
GI	gastrointestinal
GIP	glucose-dependent insulinotropic polypeptide
GLP-1	glucagon-like peptide-1
HbA1c	hemoglobin A1c
HIV	human immunodeficiency virus
IB	investigator's brochure
informed consent	A process by which a patient voluntarily confirms his or her willingness to participate in a particular study, after having been informed of all aspects of the study that are relevant to the patient's decision to participate. Informed consent is documented by means of a written, signed and dated informed consent form.
investigational medicinal product (IMP)	A pharmaceutical form of an active ingredient or placebo being tested or used as a reference in a clinical study, including products already on the market when used or assembled (formulated or packaged) in a way different from the authorized form, or marketed products used for an unauthorized indication, or marketed products used to gain further information about the authorized form.
investigator	A person responsible for the conduct of the clinical study at a study site. If a study is conducted by a team of individuals at a study site, the investigator is the responsible leader of the team and may be called the principal investigator.
legal representative	An individual or judicial or other body authorized under applicable law to consent, on behalf of a prospective patient, to the patient's participation in the clinical study.
MAD	multiple-ascending dose
OGTT	oral glucose tolerance test
PG	plasma glucose
PK/PD	pharmacokinetic/pharmacodynamic
QTc	QT corrected for heart rate
QTcF	QTc using Fridericia's formula

randomize	the process of assigning patients to an experimental group on a random basis
SAE	serious adverse event
SMPG	self-monitored plasma glucose
SC	subcutaneous
screen	The act of determining if an individual meets minimum requirements to become part of a pool of potential candidates for participation in a clinical study.
TBL	total bilirubin level
TE-ADA	treatment-emergent antidrug antibody
T2DM	type 2 diabetes mellitus
T_{max}	time to maximum drug concentration
ULN	upper limit of normal

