9.5 Safety and Tolerability Assessments

9.5.1 Adverse events

Where changes in severity are recorded in the Case Report Form (CRF), each separate severity of the AE will be reported in the listings, only the most severe will be used in the summary tables. A pre-existing condition is defined as an AE that starts before the patient has provided written informed consent and is ongoing at consent. A non-treatment emergent AE is defined as an AE which starts after informed consent but prior to dosing. A treatment-emergent AE (TEAE) is defined as an AE which occurs postdose or which is present prior to dosing and becomes more severe postdose. AEs will also be presented by day of onset.

All AEs will be listed. TEAEs will be summarized by treatment regimen, severity, and relationship to the study drug. The frequency (the number of AEs, the number of patients experiencing an AE and the percentage of patients experiencing an AE) of TEAEs will be summarized by treatment regimen, Medical Dictionary for Regulatory Activities (MedDRA) version 20.0 system organ class, and preferred term. The summary and frequency AE tables will be presented for all causalities and those considered related to the study drug. Any serious AEs will be tabulated.

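### The Safety population does not require a dose, so a patient randomised but never dosed would count in the denominator of TEAE percentages without being able to contribute an event

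*SAP*

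**What the plan says.** SAP section 8 states that the Safety "population will consist of all enrolled patients, whether or not they completed all protocol requirements". Protocol 10.3 has the same rule: "Safety analyses will be conducted for all enrolled patients, whether or not they completed all protocol requirements". The protocol synopsis repeats it.

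Protocol Appendix 1 fixes the meaning of the key word: "Patients who are enrolled in the study are those who have been assigned to a treatment". Enrolment is therefore assignment, not dosing.

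The two neighbouring definitions in SAP section 8 are narrower. The Pharmacokinetic "population will consist of all patients who received at least one dose of IMP and have evaluable PK data", and the Pharmacodynamic "population will consist of all patients who received at least one dose of IMP and have evaluable PD data".

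Adverse events are the primary endpoint (SAP 4.1). SAP 9.5.1 summarises TEAEs by regimen as number of events, number of patients and percentage of patients. A TEAE "is defined as an AE which occurs postdose or which is present prior to dosing and becomes more severe postdose". SAP 9.1 generally restricts summaries to the relevant analysis population. Protocol 10.3 groups the primary safety analyses by intended titration regimen, and SAP section 11 declares no change from the protocol's analyses.

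**The concern.** Read together, these definitions set different entry conditions for the two halves of one percentage. Assignment is enough for the denominator, but a dose is needed for the numerator. A patient who is assigned and never dosed carries no information on the safety of the drug, yet lowers the reported percentage for the regimen intended for that patient.

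In a large trial this would be invisible. Here the groups hold 9 to 16 patients, so a single such patient would show. In an active arm the direction is towards understating the event rate, in a study whose results are meant to inform dose selection for later trials in Japan (protocol 5.4 and 5.5). Other safety tables that report percentages of the Safety population, such as those for injection-site and hypersensitivity reactions (SAP 9.5.9), would be affected in the same way.

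**Working it through.** **1. Group sizes.** Protocol 10.1 and SAP section 7 give 12 active to 3 placebo in Cohorts 1 and 3, and 16 to 3 in Cohort 2.

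- Enrolled: (12 + 3) + (16 + 3) + (12 + 3) = 49, which matches the stated figure.
- Pooled placebo: 3 + 3 + 3 = 9.
- Completers at the stated drop-out rates: 15 × 0.7 + 19 × 0.5 + 15 × 0.7 = 30.5, against about 32 stated. A target of 8 completers in each of four groups gives 32 exactly, and 8/0.7 = 11.4 (rounded up to 12) and 8/0.5 = 16 reproduce the active arms. The documents do not state this derivation.

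The point at issue does not affect the sample size.

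**2. Can a patient be assigned and not dosed?** Protocol 5.1 covers the case "If the investigator decides not to administer the first dose to a patient on a particular day", following medical assessments, vital signs or ECGs; the patient may then be rescheduled. The Schedule of Activities puts randomisation, the predose checks and the first dose all on Day 1 without giving their order. Two cases follow:

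- If the dose is withheld before assignment, the patient is not enrolled under Appendix 1 and there is no effect.
- If it is withheld after assignment and the patient never returns, the patient is enrolled, belongs to the Safety population and is undosed.

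The documents do not exclude the second case and do not say how often it would arise.

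**3. Size.** Let n be the number assigned to a group and u the number never dosed. If the denominator is the Safety population of the group,

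reported percentage = percentage among dosed × (n − u)/n,

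so the relative understatement is u/n. The documents give no value for u, so it is an assumption, taken here as 0 to 2 per group.

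| Group | n | u = 0 | u = 1 | u = 2 |
|---|---|---|---|---|
| Active, Cohort 1 or Cohort 3 | 12 | 0% | 1/12 = 8.3% | 2/12 = 16.7% |
| Active, Cohort 2 | 16 | 0% | 1/16 = 6.25% | 2/16 = 12.5% |
| Pooled placebo, if undosed patients are counted in it | 9 | 0% | 1/9 = 11.1% | 2/9 = 22.2% |

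**4. The same with counts.** The event counts are assumed, for illustration only, with u = 1:

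- n = 12: 6/11 = 54.5% becomes 6/12 = 50.0%.
- n = 16: 8/15 = 53.3% becomes 8/16 = 50.0%.
- n = 9: 2/8 = 25.0% becomes 2/9 = 22.2%.

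**5. What does not move.** The number of TEAEs and the number of patients with a TEAE are the same under either definition. All adverse events are listed whether or not a dose was given.

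**The case against.** The best defence is that the case may never arise. Assignment and dosing share a day, and protocol 7.3 has the pharmacist who prepares the medication assign the treatment, which places assignment close to injection. Zero undosed patients is a natural base case. This stands, and it limits the practical weight of the point.

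A reader might infer that the protocol foresees patients who are randomised and never dosed. It does not: section 5.1 describes a delayed first dose with possible rescheduling. A reader might also infer that the primary endpoint is biased. The percentage is only one of three frequency measures, the analysis is descriptive, and the sample size has no statistical requirement, so no test, power or error rate depends on it. Nor do the documents support a claim that undosed patients would accumulate unequally by treatment within a cohort: the investigator who withholds a dose is blinded, which leaves chance. The statement that replacement is not planned concerns discontinued patients and has no bearing on the denominator.

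The placebo figure is uncertain. Protocol 10.3 and SAP section 8 pool patients treated with placebo, and an undosed patient was not treated with anything.

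Finally, SAP section 8 lets protocol deviations influence assignment to populations and allows as-treated regimen analyses after data review. This helps only in part. It is discretionary, sets no rule for undosed patients, and a first dose withheld under protocol 5.1 need not be a deviation. Protocol Appendix 8 lists the statisticians of the sponsor and the contract research organisation as unblinded from randomisation onwards, so a case-by-case exclusion could be made with the assignment known.

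**Conclusion.** The point holds as a minor defect of definition. As written, a patient assigned but never dosed belongs to the Safety population, stays in the group of the intended regimen and cannot have a TEAE. The effect depends wholly on the number of such patients. With none, there is no effect. With one, a TEAE percentage is understated in relative terms by 8.3% (n = 12), 6.25% (n = 16) or, if the pooled group includes an undosed patient assigned to placebo, 11.1% (n = 9).

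This rests on two assumptions: the value of u, and the reading of SAP 9.1 that percentages use the Safety population as denominator. The protocol and SAP agree with each other here, so this is not a contradiction between documents. The inconsistency is between the Safety definition and the definition of a TEAE.

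**What to change.** In SAP section 8, protocol 10.3 and the protocol synopsis, define the Safety population as all enrolled patients who received at least one dose of IMP. List any patient assigned but not dosed under disposition, with the reason. Report pre-dose adverse events separately; SAP 9.5.1 already defines non-treatment-emergent events and lists all adverse events, so no new data are needed.

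The cost is one clause in three places. It changes no procedure, data collection or sample size, and it brings the Safety definition into line with the dosing condition of the PK and PD populations.
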